• To collect and store DNA for future exploratory research into genes that may influence response, eg, safety, tolerability and efficacy of dapagliflozin treatment and genetic factors that may influence susceptibility to type 2 diabetes and/or associated conditions.

Study design

This is a 16-week randomised, double-blind, double dummy, placebo-controlled, 4-arm, parallel-group, multicentre study with a 4 week open label placebo lead-in period, and a 16 week treatment period. Patients will be stratified by HbA1c measurement at randomisation (HbA1c <7.0%, HbA1c \geq 7.0%). With respect to recruitment, one stratum will represent patients with an HbA1c value <7.0% (Stratum 1), up to a maximum size of 20% of all randomised patients. The other recruitment stratum (Stratum 2) consist of patients with an HbA1c value at randomisation \geq 7.0% and \leq 10.0%. Randomisation strata will be combined in the analysis of the primary endpoint.

Target subject population

Men and women with type 2 diabetes who:

- Are ≥ 18 to ≤ 77 years old at time of consenting
- Have inadequate glycaemic control, defined as HbA1c $\ge 6.7\%$ and $\le 10.5\%$ at week -4 (HbA1c $\ge 7.2\%$ and $\le 10.5\%$, after randomisation Stratum 1 complete)
- Have inadequate glycaemic control, defined as HbA1c $\geq 6.5\%$ and $\leq 10.0\%$ at week -1 (HbA1c $\geq 7.0\%$ and $\leq 10.0\%$, after randomisation Stratum 1 complete)
- Are on stable treatment with a total daily dose of immediate release formulation of metformin ≥1500 mg taken BID as monotherapy for at least 10 weeks prior to enrolment

Investigational product, dosage and mode of administration

Dapagliflozin 2.5 mg, and 5 mg tablets, administered orally twice daily, and dapagliflozin 10 mg tablet administered orally once daily, together with food and metformin.

Comparator, dosage and mode of administration

Matching placebo for dapagliflozin 2.5 mg and 5 mg administered orally twice daily as well as matching placebo for dapagliflozin 10 mg administered once daily with food and metformin.

Study drug, dosage and mode of administration

Open-label metformin IR 500 mg tablets administered orally twice daily with food to achieve total daily doses of 1500 to 2500 mg/day during the 4-week placebo lead-in period and during the 16-week double-blind treatment period.

Duration of treatment

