Following initial screening and a 1-week enrolment period, patients will enter a 4-week placebo lead-in period, after which they will be randomised to the 16-week double-blind treatment period. After either completion of the randomised treatment period or early discontinuation from treatment, patients will enter a 4-week follow-up period.

The total planned study duration starting with enrolment and including the follow-up period will be 25 weeks.

Outcome variable(s):

Primary outcome variable:

- Change in HbA1c from baseline to week 16

Key secondary outcome variables:

- Percent change in body weight from baseline to week 16
- Change in FPG from baseline to week 1
- Change in FPG from baseline to week 16
- Proportion of patients with HbA1c<7.0% at week 16, in patients who had HbA1c \geq 7.0% at baseline.

Other secondary outcome variables:

- Change in seated systolic and diastolic blood pressure (BP) from baseline to week 16
- Proportion of patients with seated systolic blood pressure <130 mmHg at week
 16 in patients who had seated systolic blood pressure ≥130 mmHg at baseline
- Change in body weight from baseline to week 16

The following secondary outcome variables apply to dapagliflozin 10 mg only:

- Change in HbA1c from baseline at week 16
- Change in FPG from baseline at week 1 and 16
- Proportion of patients with HbA1c<7.0% at week 16, in patients who had HbA1c \geq 7.0% at baseline

- Percent change in body weight from baseline to week 16
- Change in body weight from baseline to week 16
- Change in seated systolic and diastolic blood pressure (BP) from baseline to week 16
- Proportion of patients with seated systolic blood pressure <130 mmHg at week
 16 in patients who had seated systolic blood pressure ≥130 mmHg at baseline

Safety

Adverse Events (AE) laboratory values, electrocardiogram, pulse, blood pressure, hypoglycaemic events, cardiovascular events, calculated creatinine clearance, estimated glomerular filtration rate and physical examination findings.

Statistical methods

The primary outcome variable, change from baseline to week 16 in HbA1c, will be analyzed by an analysis of covariance (ANCOVA) model which will include terms for treatment group and covariate for baseline HbA1c. The ANCOVA model will be used to derive a least squares estimate of the treatment difference with 95% confidence interval and corresponding 2-sided p-value.

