5.2 Subject enrolment and randomisation

The principal investigator or delegate will:

- 1. Obtain signed informed consent from the potential patient before any study specific procedures are performed.
- 2. Perform enrolment call in Interactive Web Response System (IWRS), to obtain the unique enrolment number assigned, beginning with "E#"(E-code).
- 3. From Visit 1 to Visit 4 determine patient eligibility. See Sections 4.1 and 4.2.
- 4. Perform drug allocation call for assigning Placebo Lead-In and Metformin at Visit 2 in IWR system

The E-code will be used to identify the patient throughout study participation. Patient eligibility will be established before treatment randomisation.

Randomisation codes will be assigned strictly sequentially as patients are eligible for randomisation.

If a patient discontinues participation in the study, then his/her enrolment/randomisation code cannot be reused.

If patients have discontinued their participation in the study then they cannot re-enter into the study.

5.2.1 **Procedures for randomisation**

Randomisation to study treatment will be done via an IWRS on Visit 4, in balanced blocks in order to ensure approximate balance among treatment arms. Patients will be stratified by HbA1c at randomisation (Stratum 1, Stratum 2). The IWRS will allocate a randomisation code according to a randomisation scheme prepared by AstraZeneca.

The number and size of tablets will be identical between dapagliflozin 2.5 mg and 5 mg tablets and its matching placebo. Dapagliflozin tablets 10 mg will be identical in size and number to its matching placebo.

The size of the dapagliflozin tablets 2.5 mg and 5 mg and matching placebo (all 9 mm) is slightly smaller than the dapagliflozin tablet 10 mg and matching placebo (both 11 mm).

Patients will receive 3 bottles together with instruction to take one tablet in the morning and one tablet in the evening from the 2.5 mg, 5 mg and matching placebo bottles containing smaller tablets (with white booklet label) and 1 tablet in the morning from the 10 mg and matching placebo bottle (with yellow booklet label).

For treatment A, patients will receive dapagliflozin 2.5 mg BID and matching placebo for dapagliflozin 10 mg QD in the morning.

For treatment B, patients will receive dapagliflozin 5 mg BID and matching placebo for dapagliflozin 10 mg QD in the morning.

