Other secondary efficacy variables and safety variables shall provide supportive efficacy and safety information regarding the differences of the three dapagliflozin dose groups versus placebo.

The primary efficacy variable, change in HbA1c from baseline to week 16, will be analyzed using an analysis of covariance (ANCOVA) model with factor for treatment group (fixed effect) and covariate for baseline HbA1c. All treatment groups will be included in the model. The model will be used to derive a least squares estimate of the treatment difference in mean change with two-sided 95% confidence interval and corresponding p-value. Further, two-sided 95% confidence intervals for the mean change within each treatment group will be calculated.

The same method will be applied for analyzing other continuous efficacy variables, eg, change in systolic blood pressure from baseline to week 16. Nominal p-values for the difference of the dapagliflozin dose groups (2.5 mg BID, 5 mg BID and 10 mg QD) versus placebo will be provided.

For variables analyzed as percent change from baseline, the ANCOVA model will apply to logarithm-transformed data and resulting least-squares means and confidence intervals back-transformed to provide estimates in the original scale.

The change (or percent change) from baseline will be analyzed for important continuous efficacy variables at each scheduled time of assessment (using observed data and LOCF). For

each time point under consideration, summary statistics, adjusted mean changes (or percent changes) within each treatment group as well as means and 95% confidence intervals for the differences of the dapagliflozin dose groups (2.5 mg BID, 5 mg BID and 10 mg QD) versus placebo will be derived from an ANCOVA model with treatment group as a fixed effect, HbA1c at randomisation stratum and the baseline measurement as a covariate.

Proportions will be analyzed using the methodology of Zhang et al 2008 and Tsiatis et al 2008 when there are at least 5 subjects on average by treatment group. Estimates for treatment effects and differences between treatment groups will be obtained along with 95% confidence intervals and nominal p-values using this methodology with adjustment for baseline value. When there are less than 5 responders on average by treatment group, the unadjusted proportions and differences between proportions, exact 95% confidence intervals, and nominal p-values from the Fisher's exact test (when applicable) will be provided.

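### Section 12.2 specifies two different ANCOVA models for the same week-16 contrasts (and week-1 FPG), and does not say which one governs the continuous key secondary tests

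*Protocol*

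**What the plan says.** **Model A (no stratum).** Protocol Section 12.2 fits the primary variable, week-16 change in HbA1c, with an ANCOVA "model with factor for treatment group (fixed effect) and covariate for baseline HbA1c". The synopsis (Statistical methods) agrees: a "model which will include terms for treatment group and covariate for baseline HbA1c". Section 12.2 then adds: "The same method will be applied for analyzing other continuous efficacy variables, eg, change in systolic blood pressure from baseline to week 16". Nominal p-values against placebo are attached to this paragraph.

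**Model B (with stratum).** Two paragraphs later: "The change (or percent change) from baseline will be analyzed for important continuous efficacy variables", at each scheduled assessment, on observed and on LOCF data. The adjusted means, and the differences from placebo with 95% confidence intervals, are "derived from an ANCOVA model with treatment group as a fixed effect, HbA1c at randomisation stratum and the baseline measurement as a covariate".

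**Design.** Sections 3.1.1.4 and 5.2.1 stratify randomisation by Visit 3 HbA1c, below 7.0% or 7.0% and above, with the lower stratum capped at 20% (78 patients). The synopsis (Study design) says: "Randomisation strata will be combined in the analysis of the primary endpoint".

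**Key secondaries.** Section 12.2 lists percent weight change at week 16, FPG change at week 1, FPG change at week 16, and the proportion reaching HbA1c below 7.0%. They are tested in that order at 0.05 within each BID dose that succeeded on the primary variable, stopping at the first failure.

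**The concern.** Two specifications cover the same data and the same dapagliflozin-versus-placebo contrasts, and no sentence ranks them. For the first three key secondaries the choice decides which estimate is confirmatory. In a fixed sequence an unsettled model at the first step affects every later step, including the responder proportion, which is not itself analysed by ANCOVA.

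The model that carries the p-values also omits the factor used to stratify randomisation. For HbA1c this hardly matters, because continuous baseline HbA1c is already a covariate. For weight and FPG, if the covariate is the variable's own baseline, nothing in Model A represents the stratum. Leaving out a prognostic stratification factor tends to make standard errors slightly too large.

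**Working it through.** **1. Do the two models overlap?**

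| | Model A | Model B |
|---|---|---|
| Variables | HbA1c, then other continuous efficacy variables | Important continuous efficacy variables, change or percent change |
| Time | Week 16 (primary and the SBP example) | Every scheduled assessment |
| Data | LOCF at week 16 (Section 12.2) | Observed and LOCF |
| Terms | Treatment, baseline | Treatment, HbA1c stratum, baseline |
| Output | Difference, 95% CI, p-value | Difference, 95% CI |

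Week 16 is Visit 9 and week 1 is Visit 5 (Section 3.1.1.4 and Table 3), and FPG is measured at both (Table 7). The LOCF contrasts at week 16, and FPG at week 1, therefore fall under both columns. Model B's reference to percent change fits the weight variable at least as directly as Model A does. Model A's extension is also loose about the covariate: read literally it is baseline HbA1c; the natural reading is the variable's own baseline. Only on the natural reading is HbA1c wholly absent for weight and FPG.

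**2. The plan's own sample size.** Inputs from Section 12.3: difference 0.5, SD 0.97, two-sided 0.025, power 90%.

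n = 2 × (2.2414 + 1.2816)² × (0.97/0.5)² = 2 × 12.411 × 3.7636 = 93.4, so 94 per group by the normal approximation. With the noncentral t, power is 89.8% at 94 and 90.1% at 95, which reproduces the stated 95. Then 95/0.97 = 97.9, so 98 per group, and 4 × 98 = 392. The calculation rests on an unadjusted t-test, so the choice of ANCOVA terms changes none of these figures.

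**3. Cost in degrees of freedom.** 4 × 95 = 380 evaluable patients. Model A has 5 parameters (375 residual df); Model B has 6 (374).

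**4. Size of the effect.** Simulation with 3,000 trials per row, 95 per arm, 20% in the lower stratum, balanced within stratum.

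Assumptions not in the protocol:
- Visit 3 HbA1c is uniform on 6.5–7.0 in the lower stratum, and 7 plus a gamma variable (shape 1.8, scale 0.55, capped at 3) in the upper.
- Visit 4 baseline equals the Visit 3 value plus noise with SD 0.2.
- For HbA1c, the slope of change on baseline is 0, −0.3 or −0.5, with total SD 0.97.
- For another variable, own baseline correlates 0.5 with HbA1c, slopes per SD are −0.4 on own baseline and −0.2 on HbA1c, and residual SD is 0.97.

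| Variable, slope | True effect | SE without / with stratum | Rejected at 0.05, without / with | Calls differ at 0.05 | Calls differ at 0.025 |
|---|---|---|---|---|---|
| HbA1c, 0 | 0 | 0.1407 / 0.1408 | 4.33% / 4.27% | 0.33% | 0.17% |
| HbA1c, −0.3 | 0 | 0.1362 / 0.1362 | 5.03% / 5.00% | 0.23% | 0.07% |
| HbA1c, −0.5 | 0 | 0.1277 / 0.1277 | 5.30% / 5.10% | 0.40% | 0.03% |
| HbA1c, 0 | 0.5 | 0.1409 / 0.1410 | 93.77% / 93.87% | 0.30% | 0.30% |
| HbA1c, −0.3 | 0.5 | 0.1363 / 0.1364 | 95.33% / 95.20% | 0.33% | 0.40% |
| HbA1c, −0.5 | 0.5 | 0.1277 / 0.1277 | 97.70% / 97.70% | 0.07% | 0.37% |
| Other | 0 | 0.1430 / 0.1424 | 4.80% / 4.87% | 0.27% | 0.17% |
| Other | 0.5 | 0.1430 / 0.1424 | 93.87% / 94.03% | 0.23% | 0.57% |

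For HbA1c the two estimates differ by about 0.003 percentage points on average and 0.036 at most. For the other variable the variance ratio is (0.1430/0.1424)² = 1.008, worth under 1% of the sample size. Type I error is near nominal both ways; the Monte Carlo standard error at 5% is √(0.05 × 0.95/3000) = 0.4%.

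**The case against.** The best defence is that the documents already rank the models. P-values appear only in the Model A paragraphs, and the extension to other continuous variables covers weight and FPG. The by-visit paragraph promises means and confidence intervals, so it reads as a display over time. The synopsis also says that strata are combined for the primary endpoint, which makes the omission there look deliberate.

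Much of this stands. The primary model is stated consistently, and a reader who infers that the primary test is ambiguous or invalid goes further than the text. So does a reader who infers two p-values for each confirmatory test: Model B promises none. A reader might also suppose that switching models flips significance in several trials per hundred. That would need expected test statistics close to the critical value and correlations between the two statistics that the protocol does not give; the simulation shows far less. Nor is the absence of a treatment-by-stratum interaction a fault, since such analyses are commonly left to the SAP.

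What does not stand is that the ranking is settled for the key secondaries. The synopsis sentence covers only the primary endpoint, and combining strata is compatible with a pooled, stratum-adjusted estimate. The ranking has to be inferred from where p-values are mentioned. A Model B 95% interval also implies a decision at 0.05, the level set for the key secondaries, so the two analyses could visibly disagree at week 16. This is not detail deferred to the SAP: the protocol itself fixes both models.

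**Conclusion.** The inconsistency is real, and its numerical consequence is small. Section 12.2 gives two ANCOVA specifications for the week-16 LOCF contrasts and for week-1 FPG. It matters mainly for percent weight change and FPG at weeks 1 and 16, which are gated in sequence and whose own-baseline model has no HbA1c term.

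For the primary HbA1c test, adding the stratum changes nothing of practical note. For weight and FPG, the gain is a standard error about 0.4% smaller, and significance calls differ in well under 1% of trials. These sizes rest on the assumed baseline distributions, slopes and 0.5 correlation. The omission, where it has any effect, is conservative, so it does not threaten a positive claim. The reason to act is prespecification: the governing model for each confirmatory test should be written down before unblinding.

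**What to change.** In Section 12.2, state one ANCOVA for the primary, continuous key secondary and by-visit analyses: treatment group, HbA1c randomisation stratum (below 7.0% / 7.0% and above) and the baseline value of the analysed variable, on the log scale where the protocol already requires that for percent change. Replace the loose extension to other continuous variables with this wording, so that the covariate is explicit. Label any stratum-free model as supportive.

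Align the synopsis: add the stratum to its model statement, and reword the sentence on combining strata to say that one pooled, stratum-adjusted treatment effect is estimated.

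The cost is one degree of freedom (375 to 374) and a few sentences. The sample size of 95 evaluable and 98 randomised per group, 392 in total, is unchanged.

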To compare the change from baseline in HbA1c achieved with each of the 2 BID doses of dapagliflozin (2.5 mg BID and 5 mg BID) co-administered with metformin versus placebo co-administered with metformin after 16 weeks of double-blind treatment.

"BID" means twice daily administration. Baseline is defined as the last value collected on/or prior the date of the first dose of the double-blind study. It is expected that baseline value is from the randomisation visit (Visit 4), at week 0. Metformin-IR means that immediate release formulation tablets of metformin will be administered BID, however "metformin" will be used throughout the protocol text.

Key Secondary Objectives

- To compare the percent change from baseline in body weight achieved with each of the 2 BID doses of dapagliflozin (2.5 mg BID, and 5 mg BID) co-administered with metformin versus placebo co-administered with metformin after 16 weeks of double-blind treatment.
- To compare the change from baseline in fasting plasma glucose (FPG) achieved with each of the 2 BID doses of dapagliflozin (2.5 mg BID and 5 mg BID) co-administered with metformin versus placebo co-administered with metformin after 1 week of double-blind treatment.
- To compare the change from baseline in fasting plasma glucose (FPG) achieved with each of the 2 BID doses of dapagliflozin (2.5 mg BID and 5 mg BID) co-administered with metformin versus placebo co-administered with metformin after 16 weeks of double-blind treatment.
- To compare the proportion of patients with HbA1c <7.0% achieved with each of the 2 BID doses of dapagliflozin (2.5 mg BID and 5 mg BID) co-administered with metformin versus placebo co-administered with metformin after 16 weeks of double-blind treatment, in patients who had HbA1c ≥7.0% at baseline.

Other Secondary Objective

Efficacy

- To compare the change from baseline in seated systolic and diastolic blood pressure (BP) achieved with each of the 2 BID doses of dapagliflozin (2.5 mg BID and 5 mg BID) co-administered with metformin versus placebo co-administered with metformin after 16 weeks of double-blind treatment.
- To compare the proportion of patients with seated systolic blood pressure <130 mmHg reached with each of the 2 BID doses of dapagliflozin (2.5 mg BID and 5 mg BID) co-administered with metformin versus placebo co-administered with metformin after 16 weeks of double-blind treatment, in patients who had seated systolic blood pressure ≥130 mmHg at baseline.

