During the placebo lead-in period, background antihypertensive medications should be adjusted in patients with seated systolic BP \geq 160 mmHg or seated diastolic BP \geq 100 mmHg. Only those patients with seated systolic BP <160 mmHg and diastolic BP <100 mmHg at the end of placebo lead-in period will be randomised.

At Visit 3 assessments are performed primarily to check eligibility for randomisation, following one week later. HbA1c, FPG and CK measured by the central laboratory in a sample taken at Visit 3 will be used for assessment of corresponding eligibility criteria at randomisation.

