3.2.3 Choice of outcome variables

HbA1c is the variable of choice for assessment of glycaemic control and is required for registration purposes, but fasting plasma glucose will also be measured at each visit.

Because of its novel, complementary mechanism of action, dapagliflozin may have additive or synergistic HbA1c-lowering effects when given in combination with other antihyperglycaemic agents. Additionally, as beneficial effects on weight, systolic blood pressure (SBP) and FPG have been observed in other dapagliflozin studies, these variables have been chosen as key and non-key secondary objectives (see Table 4).

| Efficacy variable | Related objective | Rationale |
|-------------------|--|--|
| HbA1c | Change in HbA1c from baseline at week 16. Proportion of patients with HbA1c <7.0% at 16 weeks, in patients who had HbA1c ≥7.0% at baseline. | HbA1c is the clinical and regulatory parameter used to estimate glycaemic efficacy in patients with type 2 diabetes (CPMP 2002). HbA1c targets for patients with type 2 diabetes range from <6.5% (IDF 2005, AACE 2007) to <7.0% (ADA 2009, ADA 2010). The degree of change in HbA1c in patients with type 2 diabetes is related to the baseline HbA1c level; patients with higher HbA1c at baseline tend to have greater reductions in HbA1c when treated with any antihyperglycaemic agent (Bailey 2010, Bloomgarden 2006) |

Table 4Efficacy variables with related objectives and rationale

| Efficacy variable | Related objective | Rationale |
|------------------------|--|--|
| Fasting Plasma Glucose | Change in FPG from baseline at week 1. Change in FPG from baseline at week 16. | Fasting plasma glucose is a well-established measure of glycaemic efficacy, and is considered by the CHMP (Committee for Medicinal Products for Human Use) to be acceptable as secondary endpoint (CPMP 2002). |
| Weight | Percent change in body weight from baseline at week 16. Change in body weight from baseline at week 16. | More than 85% of patients with T2DM are overweight (BMI $\geq 25 \text{ kg/m}^2$) or obese (BMI $\geq 30 \text{ kg/m}^2$) (CDC 2004). Weight loss is a fundamental goal for the majority of patients with type 2 diabetes since it has been shown to improve comorbid conditions such as hypertension, dyslipidemia, heart disease, osteoarthritis, and sleep apnea |

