5. STUDY CONDUCT

5.1 **Restrictions during the study**

All patients will visit the clinic fasting, in the morning, before 11 a.m. if possible. Patients will be instructed to abstain from all food and beverages for 12 hours prior to each clinic visit (drinking water is allowed). Permitted medications may be taken with water only.

Patients should not drink alcohol within 24 hours prior to each visit and should not use tobacco/nicotine within 12 hours prior to each visit.

Patients should not take investigational product or open-label metformin on the morning of the clinic visit. These medications should be taken with their first meal of the day.

If a patient arrives for a visit without having followed the above instructions, the entire visit should be rescheduled (within the allowed time-window, if possible).

Approximately 152 ml of blood will be drawn from each patient during the entire duration of the clinical study (excluding optional genetic blood sample and extra blood samples taken at unscheduled visits), patients should be instructed to abstain from donating any blood during the clinical study and for 3 months following their last study visit.

Prohibited and restricted concomitant medications are listed in Sections 4.2 and 4.3.1. Fasting prior to laboratory assessments is described in Section 6.4.6.

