11.2.1 Change and percent change from baseline

Change from baseline will be calculated as absolute difference between the value measured at or derived for a specific time point after baseline minus baseline value. Baseline is defined as the last value collected on/or prior the date of the first dose of the double-blind study

Percent change from baseline will be computed as 100*(value measured at or derived for a specific time point after baseline - baseline value)/baseline value.

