12.2 Methods of statistical analyses

All efficacy analyses will be based on the Full Analysis Set. The primary efficacy variable of change from baseline in HbA1c will also be analyzed using the Per-Protocol Analysis Set if more than 10% of the subjects in any regimen are found to significantly violate the terms and

conditions of the protocol (see description of Per-Protocol Analysis Set). Treatment effects will be determined through pair-wise treatment group comparisons: each dapagliflozin dose group versus placebo. No statistical comparisons will be made amongst the three dapagliflozin groups (2.5 mg BID, 5 mg BID and 10 mg QD).

The dapagliflozin 10 mg QD treatment group is provided as a measure of assay sensitivity. Comparisons of dapagliflozin 10 mg QD to placebo will be performed with nominal p values, outside of the controls, for multiplicity for the two dapagliflozin BID groups.

For efficacy variables, missing values at week 16 will be replaced by the last observation carried forward (LOCF) approach (see 11.2.2).

The primary objective of the study is to assess the efficacy of dapagliflozin 2.5 mg BID and 5 mg BID compared to placebo as add-on therapy to metformin in improving glycaemic control in subjects with type 2 diabetes, as determined by the primary efficacy variable change in HbA1c from baseline to week 16.

The null hypotheses H_{01} and H_{02} given below will be tested against the alternative hypotheses H_{A1} and H_{A2} respectively ($\alpha \le 0.050$, two-sided):

| $H_{01}: \mu_{D1} - \mu_P = 0,$ | H ₀₂ : $\mu_{D2} - \mu_P = 0$, |
|-------------------------------------|--|
| $H_{A1}: \mu_{D1} - \mu_P \neq 0,$ | $H_{A2}: \mu_{D2} - \mu_P \neq 0,$ |

where μ_{D1} and μ_{D2} denote the mean change in HbA1c from baseline to week 16 in the two dapagliflozin dose groups (2.5 mg BID and 5 mg BID) and μ_P denotes the mean change in HbA1c from baseline to week 16 in the placebo group. D1 denotes the dapagliflozin 2.5 mg BID dose group, and D2 denotes the dapagliflozin 5 mg BID dose group

The following key secondary efficacy variables have been identified:

- 1. Percent change in body weight from baseline to week 16
- 2. Change in FPG from baseline to week 1
- 3. Change in FPG from baseline to week 16
- 4. Proportion of patients with HbA1c<7.0%, in patients with HbA1c \geq 7.0% at baseline.

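### The FPG analyses adjust for the Visit 4 value only; adding the Visit 3 FPG, already drawn, as a second covariate is an optional precision gain, not a correction of an error

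*Protocol*

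**What the plan says.** Protocol section 12.2 specifies, for HbA1c, an "analysis of covariance (ANCOVA) model with factor for treatment group (fixed effect) and covariate for baseline HbA1c". It then says: "The same method will be applied for analyzing other continuous efficacy variables". FPG is such a variable, so its model has treatment and one baseline FPG. A separate by-visit model in the same section adds the HbA1c randomisation stratum, again with a single baseline measurement.

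Section 11.2.1 fixes which value that is: "Baseline is defined as the last value collected on/or prior the date of the first dose of the double-blind study". The synopsis adds: "It is expected that baseline value is from the randomisation visit (Visit 4), at week 0".

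FPG is also available earlier. Section 3.2.3 says that "fasting plasma glucose will also be measured at each visit", and Table 7 (section 6.3) marks Visits 1, 2, 3 and 4 before dosing. Section 3.1.1.3 gives the use of the Visit 3 sample: "HbA1c, FPG and CK measured by the central laboratory in a sample taken at Visit 3 will be used for assessment" of eligibility. Fasting conditions are common to all visits (section 5.1): "All patients will visit the clinic fasting, in the morning, before 11 a.m. if possible".

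"Change in FPG from baseline to week 1" is second, and the week 16 change third, of the four key secondary variables in section 12.2. They are tested in fixed order at 0.05 within each BID dose, and inference in a dose stops at its first failed test.

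**The concern.** One fasting glucose is an imperfect measure of a patient's usual level. Visit 3 falls one week before Visit 4, under the same fasting rule, with the same central laboratory, sponsor-supplied metformin and placebo tablets. It is close to a replicate of the baseline, taken before randomisation. Used as a second covariate, it may explain between-patient variation that the Visit 4 value misses, and it cannot bias the treatment difference because it precedes treatment.

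Precision matters here because the two FPG tests sit in the middle of the sequence. A miss at week 1 ends inference for that dose before FPG at week 16 and the HbA1c <7.0% responder comparison. A miss at week 16 ends it before the responder comparison. The sample size in section 12.3 was set for HbA1c only, and no power is stated for FPG.

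**Working it through.** **The plan's own sample size.** Section 12.3 uses a difference of 0.5, SD 0.97, two-sided alpha 0.025 and 90% power. The exact two-sample t-test has power 0.898 with 94 per group and 0.901 with 95, so 95 reproduces. 95/0.97 = 97.9, i.e. 98 per group; 4 × 98 = 392; 392/0.6 = 653.3, i.e. 654. None of this concerns FPG.

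**Inputs for the FPG check.** The protocol gives no FPG SD, effect or correlation. Three correlations among randomised patients are therefore assumed:

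- r: Visit 3 FPG with Visit 4 FPG
- p4: Visit 4 FPG with on-treatment FPG
- p3: Visit 3 FPG with on-treatment FPG

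**Formula.** With Visit 4 as a covariate, analysing the change from Visit 4 or the on-treatment value gives the same treatment difference and the same residual variance. As a share of the on-treatment variance, that residual is 1 − p4² with Visit 4 alone. Adding Visit 3 multiplies it by

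ratio = 1 − (p3 − r·p4)² / [(1 − r²)(1 − p4²)].

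If all three correlations equal r, this reduces to (1 + 2r)/(1 + r)².

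**Week 1, Visit 3 as predictive as Visit 4 (p3 = p4 = r).**

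| r | ratio | variance cut |
|---|---|---|
| 0.5 | 0.889 | 11.1% |
| 0.6 | 0.859 | 14.1% |
| 0.7 | 0.830 | 17.0% |
| 0.8 | 0.802 | 19.8% |
| 0.9 | 0.776 | 22.4% |

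Example: r = 0.7 gives 2.4/2.89 = 0.830.

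**Week 1, Visit 3 slightly less predictive (p4 = r, p3 = r − 0.05).** Visit 3 is two weeks before the week 1 sample and Visit 4 only one, so some loss is plausible. For r = 0.5, 0.6, 0.7, 0.8 and 0.9 the ratios are 0.929, 0.912, 0.902, 0.907 and 0.956, i.e. cuts of 7.1, 8.8, 9.8, 9.3 and 4.4%. Example: r = 0.7 gives 1 − 0.16²/0.2601 = 0.902.

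**Week 16 (p3 = p4 = 0.3 to 0.6, r = 0.6 to 0.9).** The ratio runs from 0.995 (r = 0.9, p = 0.3) to 0.859 (r = 0.6, p = 0.6), i.e. cuts of 0.5 to 14%. A middle case, r = 0.7 and p = 0.5, gives 1 − 0.15²/0.3825 = 0.941, a cut of 5.9%.

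**No-gain case.** Under pure first-order decay p3 = r·p4. The numerator is zero and the ratio is 1.00.

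**Averaging instead of adding.** If the mean of Visits 3 and 4 replaces Visit 4 as the covariate, the residual is 1 − [(p3 + p4)/2]² / [(1 + r)/2]. Relative to Visit 4 alone, the variance ratio is 1.02 at r = 0.9 with the 0.05 loss. It is 1.08 to 1.18 under first-order decay with r = 0.5 to 0.8. Averaging can therefore lose precision.

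**Power.** New power = Φ[(1.96 + z)/√ratio − 1.96], where z is the normal quantile of the starting power at two-sided 0.05. Every starting power is an assumption.

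| Starting power | Week 1, ratio 0.830 | Week 1, ratio 0.902 | Week 16, ratio 0.941 |
|---|---|---|---|
| 80% | 86.7% | 83.9% | 82.3% |
| 90% | 94.5% | 92.7% | 91.6% |
| 95% | 97.7% | 96.7% | 96.0% |
| 99% | 99.7% | 99.5% | 99.3% |

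**The case against.** The strongest objection is that nothing here is wrong. ANCOVA on the last pre-dose value is standard, unbiased and keeps the error rate, and a second covariate could be left to the SAP that section 12 promises before unblinding. The first part stands in full. The second stands only in part, because section 12.2 does name the covariate for these tests.

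A reader might infer that the FPG steps are underpowered and endanger the later claims. The documents do not support that. Section 1.1 reports clear FPG reductions across the Phase IIb dose range and similar findings as add-on to metformin. The trial is sized for HbA1c at alpha 0.025, while the key secondary tests use 0.05. From a start of 95% or 99% the gain is a few points or less.

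A reader might also infer that the interval is bound to narrow, or that the week 1 gain is at least 10%. Neither follows. Those readings need Visit 3 to predict the outcome as well as Visit 4 does. If its correlation is 0.05 lower, the cut is about 4-10%. If it is 0.10 lower, the cut is 0.3-5%. Under first-order decay it is zero.

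Two smaller points stand. The by-visit model already carries some Visit 3 glycaemic information through the binary HbA1c stratum, so its gain may be less than computed against Visit 4 alone. The scope is also a choice: FPG is drawn at Visits 1 and 2 as well, and HbA1c and weight also have Visit 3 values. Among the earlier FPG samples, however, only Visit 3 is taken after patients have been on study metformin and placebo tablets.

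**Conclusion.** The point holds as an optional efficiency improvement. The planned FPG analysis is valid, and no result would be biased by leaving it unchanged. Adding the Visit 3 FPG is expected to cut the residual variance by roughly 4-22% at week 1 and about 0.5-14% at week 16. It gains nothing if Visit 3 adds no information beyond Visit 4, and less than 4% at week 1 is possible if the Visit 3 correlation falls off faster than the mild case above. These ranges rest entirely on assumed correlations. The benefit is plausibly worthwhile at week 1, probably small at week 16, and small in power terms at either time if the FPG effect is already well powered.

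**What to change.** In section 12.2, and in the SAP before unblinding, add one sentence: the FPG ANCOVAs (week 1, week 16 and by visit) include the Visit 3 FPG as a second pre-randomisation covariate alongside the Visit 4 FPG, with the Visit 4 value substituted where Visit 3 is missing. Keep the section 11.2.1 baseline definition, the change-from-Visit-4 outcome and the HbA1c stratum in the by-visit model. Do not replace the baseline by the mean of the two visits.

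The cost is one residual degree of freedom. With 380 evaluable patients (4 × 95), four treatment groups and one covariate, 375 remain under the current main model and 374 after the change. No new samples, patients or endpoint definitions are needed.
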